9.4.1.2. Serious Adverse Event (SAE)

An SAE or reaction is any adverse drug experience occurring at any dose that results in any of the following outcomes:

- Death
- Is life-threatening (at the time of the event)
- Requires inpatient hospitalization or prolongation of existing hospitalization,
- Results in persistent or significant disability/incapacity
- Is a congenital anomaly/birth defect (in an offspring)

- An Important medical event that may not result in death, be life-threatening, or require hospitalization may be considered an SAE when, based upon appropriate medical judgment, the event may jeopardize the subject and/or may require medical or surgical intervention to prevent one of the outcomes listed in this definition.

All AEs requiring hospitalization or prolongation of a pre-existing hospitalization should be reported as SAEs unless they occur greater than 14 days after the Follow-up Visit (or 30 days after early termination) AND are not considered to be drug-related by the Investigator.

Hospitalizations meeting the following criteria will not be reported as an SAE but must be recorded on the appropriate CRF: study specified hospitalization, short-term administrative hospitalization for procedures, tests or treatments of conditions that would not otherwise constitute an SAE, elective hospitalizations.

9.4.1.2.1. Serious Adverse Event Reporting

Serious AEs must be reported to the Sponsor or designee within 24 hours of knowledge of the event. All SAEs that occur while a subject is receiving study drug and within 14 days following the Follow-up Visit (or 30 days after early termination) are reportable within 24 hours. During the follow-up period beyond 14 days from Follow-up (or 30 days after early termination), only those SAEs that are considered to be possibly related to study drug should be reported within 24 hours.

The procedure for reporting an SAE is as follows:

- Within 24 hours of knowledge of the event, the site must contact the Sponsor (or designee) by telephone or facsimile to report the event.
- The initial report should include all information known at the time of the report (additional information can be reported as discovered). Do not delay the initial reporting in order to obtain resolution or follow-up information.
- The site will enter into the electronic database (or fax, if the database cannot be accessed for any reason) an SAE report, or similar form, that includes the following information, as available:
 - Subject ID
 - Basic demographic information (age, gender, weight)
 - Outcomes attributed to the event (death, life-threatening hospitalization [new or prolonged], disability, congenital anomaly, required medical intervention to prevent permanent impairment/damage, etc.)
 - Onset date and severity of the event
 - Brief description of the event including frequency and severity of symptoms leading to diagnosis
 - List of relevant test results and laboratory data
 - Any other relevant history
 - Whether the study drug was discontinued

- Whether the assigned treatment oral or injectable therapy was discontinued and/or dose titration discontinued, as applicable
- Investigator's assessment of causality

The Medical Monitor or another representative of the Sponsor may contact the Investigator to request additional information regarding the event or to confirm information. All SAEs will be entered on the AE CRF. The same nomenclature should be used on both the SAE report and the AE CRF.

Specific instructions for SAE reporting and a copy of an SAE report form are provided in the MOP.

The Investigator is responsible for the complete and timely reporting of all SAEs to the Sponsor (or designee), reporting pertinent follow-up information on the SAE, and notifying the appropriate IRB/Independent Ethics Committee (IEC) of the occurrence of and details surrounding the event. In the event there is a question as to whether the AE is serious, the event should be reported.

9.4.1.2.2. Suspected Unexpected Serious Adverse Reaction

A suspected unexpected serious adverse reaction (SUSAR) is defined as an SAE and where:

- There is a certain degree of probability that the event is harmful, and an undesirable, reaction to the medicinal product being research, regardless of the administered dosage. In other words, there is an adverse reaction.
- The adverse reaction is unexpected. That is to say, the nature and severity of the adverse reaction are not in agreement with the reference safety information as recorded in the Investigator's Brochure.

A SUSAR has additional reporting requirements, as described below.

- If the SUSAR is fatal or life-threatening, associated with the use of the investigational medicinal product, and unexpected, competent authorities and ethics committees will be notified within 7 calendar days after the Investigator learns of the event. Additional follow-up information (cause of death, autopsy report, hospital report) should be reported within an additional 8 days (15 days in total).
- If the SUSAR is not fatal or life-threatening but is otherwise serious, associated with the use of the investigational medicinal product, and unexpected, competent authorities and ethics committees will be notified within 15 calendar days after the Investigator learns of the event.

All Investigators will receive relevant information about SUSARs in a timely fashion. Follow-up information may be submitted if necessary.

9.4.2. Pregnancy

Pregnancies among trial participants or their partners should be reported to the Sponsor or designee as soon as possible after learning of the event. Subjects who become pregnant may withdraw their consent and discontinue the study and be referred back to the care of their usual provider or continue in the study after discussion with and documentation by the Principal

Investigator or his/her designee. (In the UK, participants who become pregnant will be discontinued from the study permanently and be referred back to the care of their usual provider.) Follow-up information will be obtained where possible (with the consent of the participant or their partner) regarding the course and outcome of the pregnancy, including any post-natal sequelae in the infant during the first year of life.

9.4.3. Clinical Laboratory Assessments

All protocol-specified laboratory tests on blood and urine samples will be performed at a selected central laboratory, with the exception of urine pregnancy tests that are conducted at the study site. The central lab will generate laboratory reports and forward them to the clinical site in a timely manner. It is the responsibility of the Investigator to review and sign all lab reports expeditiously, in order to document appropriate safety monitoring of study subjects. The Investigator should sign and date each lab report concurrent with her or his review, and should indicate the clinical significance of each abnormal/flagged value by noting “NCS” (not clinically significant) or “CS” (clinically significant), for example. Notations indicating that a value is clinically significant should also include a brief description of the underlying disease or condition that is associated with the value, e.g., “CS/mild anemia.” Per investigator judgment, abnormal, clinically significant laboratory values are expected to be associated with an item recorded in medical history or with an AE.

Blood and urine samples will be collected, processed, and shipped according to instructions from the safety laboratory. Additional laboratory samples may be taken at the discretion of the Investigator if the results of any tests fall outside reference ranges or clinical symptoms necessitate testing to ensure safety. Specific hematology, coagulation, biochemistry, and urinalysis assessments are listed in [Table 4](#).

Table 4: Clinical Laboratory Assessments

Hematology	Biochemistry	Urinalysis
Hematocrit	Sodium	Color
Hemoglobin	Potassium	pH
Red blood cell (RBC) count	Magnesium	Specific gravity
RBC Morphology	Calcium	Ketones
Mean corpuscular volume	Glucose (random)	Protein
Mean corpuscular hemoglobin	Bicarbonate	Glucose
Mean corpuscular hemoglobin concentration	Chloride	Bilirubin
Total and differential (absolute) white blood cell count	Creatinine	Nitrite
Platelets	Total protein	Urobilinogen
	Blood urea nitrogen	Occult blood
	Albumin	Microscopic examination of sediment, only if urinalysis dipstick results are abnormal
	Total bilirubin	
	Alanine transferase	
	Aspartate transferase	
	Lactic dehydrogenase	
	Amylase	
	Lipase	
	Gamma-glutamyl transferase	
	Alkaline phosphatase	
	Creatine phosphokinase	
	Total cholesterol (non-fasting)	
Coagulation		
Prothrombin time (PT), International normalized ratio (INR)		

In addition to the clinical laboratory tests, a serum pregnancy test will be performed at the Screening Visit and the End of Treatment Visit. An “in-office” urine pregnancy test will be required at Day 1 PRIOR to first CAM2038 administration, and then at each visit prior to administration of CAM2038 (for women of childbearing potential). Results must be reviewed and confirmed to be negative prior to start of CAM2038 treatment (Day 1).

A blood sample for a serology panel testing for hepatitis B surface antigen, anti-hepatitis C antibodies, and HIV will be performed for all subjects, unless a site’s IRB prohibits such testing. It is the Investigator’s responsibility to understand and comply with all laws and regulations that apply to the testing of blood for HIV and hepatitis B and C. These laws and regulations may include state laws related to written consent, separate from the ICF for this study, and pre- and post-test counseling.

9.4.4. Vital Signs

Vital signs will consist of temperature, blood pressure (systolic and diastolic blood pressure, mmHg), pulse rate (beats per minute), and respiratory rate (breaths/min) collected while sitting, following a rest period of at least 3 minutes.

9.4.5. 12-Lead Electrocardiogram (ECG)

12-Lead ECGs will be performed after the subject has been resting in a recumbent/supine position for at least 3 minutes. The ECG variables will include ventricular heart rate and the PR, QRS, QT, QTcB and QTcF intervals. The ECGs will be signed and dated by a medically-qualified individual to confirm review of the ECG and verify whether any abnormalities are clinically significant. In general, abnormal, clinically significant ECGs are expected to be associated with an item recorded in medical history or with an AE.

ECGs will be performed at Screening and at the EOT visit. In addition, ECGs will be performed after the first administration of CAM2038 q1w or CAM2038 q4w (i.e., prior to dosing at Week 2 for CAM2038 q1w or Week 5 for CAM2038 q4w). ECGs will also be performed in connection to dose increases (excluding the initial dose titration and booster injections) and after intake of QT-extending drugs or CYP3A4 inhibitors (a list of relevant drugs will be included in the Study MOP).

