Figures below are geometric mean observed steady state C_{max} and C_{trough} for Subutex from HS-11-426 and HS-13-487; Predicted plasma concentration versus time profiles for CAM2038 q1w from single and repeat dose data in HS-13-487; Observed steady state plasma concentration versus time profiles for CAM2038 q1w 16 mg from HS-13-487; and Predicted steady state plasma concentration versus time profiles for CAM2038 q4w from single-dose data in HS-13-487.

Figure 1: Observed and Predicted Plasma Concentration Versus Time Profiles for CAM2038

[figure not shown]

Figure 2: Predicted Plasma Concentration Versus Time Profiles For CAM2038

[figure not shown]
[figure not shown]

Figure 3: Predicted Plasma Concentration Versus Time Profiles For CAM2038

The following table demonstrates the estimation of plasma buprenorphine levels during the induction treatment with CAM2038 q1w. These plasma levels provide a rationale that induction treatment with CAM2038 q1w may mimic the gradual increase in the plasma buprenorphine levels provided with titration methods with SL BPN.

Table 1: Plasma Concentrations of Buprenorphine (Geometric Mean) After Single Subcutaneous Administration of CAM2038 q1w to Healthy Subjects Under Naltrexone Blockage

Time after dose (h)	Plasma concentrations of buprenorphine (ng/mL)		
	CAM2038 q1w 8 mg	CAM2038 q1w 16 mg	CAM2038 q1w 32 mg
Pre-dose	<0.025	<0.025	<0.025
0.5	0.0759	0.253	0.220
1	0.119	0.396	0.391
2	0.257	0.722	0.748
4	0.568	1.39	1.83
6	0.767	1.63	2.61
10	1.40	2.84	4.42

24	1.65	2.84	5.00
36	1.11	2.02	3.76

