5.4. Overall Risk Benefit Assessment

BPN is a substance with well-established use in the treatment dependence on opioid drugs. The CAM2038 products contain BPN in a new FluidCrystal (FC) formulation for subcutaneous (SC) injection. Clinical trials have demonstrated effectiveness of BPN in reducing illicit opioid use and improving retention rates of patients in outpatient maintenance treatment of opioid dependence, as well as substantial reduction in criminal activity, deaths, and HIV transmission. The need for daily administration of SL BPN may negatively influence patients' compliance and BPN tablets or film can be easily diverted for illicit use, injected for greater effect, or accidentally ingested, especially by children.

CAM2038 q1w and CAM2038 q4w are ready-to-use, SC BPN FC Injection depots that are being developed as alternative dosage form for treatment of opioid drug dependence by providing extended BPN release at target plasma concentrations over the weekly and monthly dosing intervals, respectively. Due to the fact that CAM2038 products need to be administered by a clinician, CAM2038 products cannot be abused or diverted by patients. In addition, it may decrease the tendency for patients to request unnecessarily high BPN doses. It will also ensure that the dose required is the dose received. Compared with the sublingual buprenorphine products on the market, CAM2038 q1w and CAM2038 q4w have several potential advantages: 1) rapid therapeutic onset (with maximum plasma concentrations established within 24 hours after injection) followed by steady long-acting release; 2) reduced variation in buprenorphine plasma levels over time (stable plasma levels attained for at least 28 days (CAM2038 q4w) and 7 days (CAM2038 q1w) resulting in more consistent therapeutic plasma levels and a possible reduction in morning "cravings"; 3) less frequent dosing resulting in reduced frequency of clinic visits and need for medical support; 4) significantly higher bioavailability, meaning less drug substance in circulation and on the street; 5) decreased risk of drug diversion; and 6) easier dose adjustment.

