7.1.2. Treatment Phase (Week 1 to Week 48)

7.1.2.1. Day 1 (Week 1) (CAM2038 q1w)

New entrants to BPN Treatment: On Day 1, for subjects who are **not currently receiving SL BPN or buprenorphine/naloxone (SL BPN/BPX)**, treatment will be initiated with CAM2038 q1w in the following manner:

Day 1: On Day 1, subjects will receive the following, while on site:

- A 4 mg SL BPN tablet test dose and observed for at least 1 hour prior to study drug administration.
- Once tolerability is confirmed (i.e., no precipitated withdrawal symptoms), a single CAM2038 q1w (once-weekly) 16 mg injection (0.32 mL of active) will be administered.

Day 2: All subjects will return to the clinic on Day 2 to ensure tolerability.

Day 4: All subjects will return to the clinic. Subjects who return on Day 4 still experiencing withdrawal symptoms should receive a single CAM2038 q1w 8 mg SC injection (0.16 mL of active). A visit window of

±1 day is allowed for the Day 4 visit.

Days 5 to 7: Subjects requiring additional dosage adjustments may return to the clinic on Days 5 to 7 if needed, based on withdrawal symptoms or tolerability. Subjects who require additional increases in dose will receive up to two additional CAM2038 q1w 8 mg SC injections (0.16 mL of active) (i.e., up to a maximum of 40 mg SC injection dose per week).

Subjects Currently on Weekly BPN Treatment: Subjects who are **currently receiving SL BPN/BPX** and are considered a candidate for CAM2038 q1w treatment by the Investigator will be transitioned to CAM2038 q1w in the following manner:

- Subjects will receive a single CAM2038 q1w SC injection that corresponds to their current SL BPN/BPX dose prior to Day 1:
 - ≤ 6 mg SL BPN/BPX: 8 mg (0.16 mL) CAM2038 q1w SC injection
 - 8-10 mg SL BPN/BPX: 16 mg (0.32 mL) CAM2038 q1w SC injection
 - 12-16 mg SL BPN/BPX: 24 mg (0.48 mL) CAM2038 q1w SC injection
 - 18-24 mg SL BPN/BPX: 32 mg (0.64 mL) CAM2038 q1w SC injection

- Subjects may return to the clinic for additional titration with CAM2038 q1w (8 mg SC booster injections), as needed, up to a maximum weekly dose of 40 mg per week.

Subjects should not take their ordinary SL BPN tablet(s) on Day 1 (i.e., the last dose of SL BPN should be taken on the day before dosing with CAM2038 q1w).

Subjects will return to the clinic for weekly visits during which they will receive their CAM2038 q1w SC injection treatments.

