^m A complete physical exam of all major body systems will be performed at the Screening Visit.

Study Phase:	Screening	Treatment Phase						EOT	Follow-up	
Treatment:	-	CAM2038 q1w or q4w	CAM2038 q1w			CAM2038 q4w				All Subjects
Study Population:	All Subjects ^a	All Subjects	New to BPN Treatment ^b	Transition from SL BPN/BPX ^c	Transition from CAM2038 q1w ^d	Transition from SL BPN/BPX (Monthly) ^e				
Month ^f :	M-1	M1	M1	M1 to Mx	M1 to Mx	Mx to M12 ^g	M1 to M12 ^h		M13	
Week ^h :	-3	W1	W1	W2 to Wx ⁱ	W1 to Wx ⁱ	Wx to W48	W1 to W48		W49	
Day:	-	Day 1	Day 2-7 ^j	-	-	-	-		-	
Weight, BMI	X	X		Monthly	Monthly	Monthly	Monthly			
Height	X									
Abbreviated Review of Systems		X							X	
Vital Signs ⁿ	X	X		Weekly	Weekly	Monthly	Monthly		X	
ECG	X			X ^o	X ^o	X ^o	X ^o		X	
Laboratory tests ^p	X								X	
Pregnancy Test ^q	X	X		Weekly	Weekly	Monthly	Monthly		X	
Hepatitis B/C, HIV ^r	X									
Injection Site Examination		X		Weekly	Weekly	Monthly	Monthly		X	
Dispense Treatment ID Card		X								
Urine Toxicology	X	X		Weekly	Weekly	Monthly	Monthly		X	
Illicit Drug Use Self-Report	X	X		Weekly	Weekly	Monthly	Monthly		X	
SOWS, COWS VAS	X	X	(X)	Monthly	Monthly	Monthly	Monthly		X	
EQ-5D-5L	X	X		Monthly	Monthly	Monthly	Monthly		X	

ⁿ Includes temperature, blood pressure, pulse rate, respiration rate.

^o ECG will be performed after the first administration of CAM2038 q1w or CAM2038 q4w (i.e., prior to dosing at Week 2 for CAM2038 q1w or Week 5 for CAM2038 q4w). During the study, ECGs will be performed after dose increases (excluding the initial dose titration and booster injections) and after intake of QT-extending drugs or CYP3A4 inhibitors.

^p Includes chemistry, hematology, urinalysis and coagulation profile.

^q A serum pregnancy test will be performed at Screening and EOT (Week 49). An “in-office” urine pregnancy test will be required at Day 1 PRIOR to the first injection of CAM2038 and then at each visit thereafter (for women of childbearing potential).

^r It is the Investigator’s responsibility to understand and comply with all laws and regulations that apply to HIV, Hepatitis B, and Hepatitis C and testing of blood. Hepatitis B/C and HIV testing is required unless a site’s IRB prohibits such testing.

Study Phase:	Screening	Treatment Phase						EOT	Follow-up
Treatment:	-	CAM2038 q1w or q4w	CAM2038 q1w			CAM2038 q4w			All Subjects

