11.1.5 PHYSICAL EXAMINATION

Physical examination data at Screening will be summarized.

11.1.6 12-LEAD ELECTROCARDIOGRAM

12-Lead ECGs will be assessed over time. The ECG variables will include ventricular heart rate and the PR, QRS, QT, QTcB and QTcF intervals. The ECGs will be signed and dated by a medically-qualified individual to confirm review of the ECG and verify whether any abnormalities are clinically significant.

Number and percent of patients in each ECG finding category (normal, abnormal not clinically significant, and abnormal and clinically significant), will be summarized for each visit. Summary statistics will be presented for the actual value and change for each ECG parameter.

The number and percent of patients with QT, QTcB and QTcF intervals < 450 msec, 450 to <480, 480 to <500 and greater than/equal to 500 msec at each visit and overall (at any visit) will be summarized. Additionally, the number and percentage of patients with increases in these parameters of <30 msec, 30 to <60 msec and greater than/equal to 60 msec will be summarized at each visit.

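### No ECG or vital-sign set is scheduled at the stated buprenorphine peak or labelled by time since injection, and the SAP gives no any-visit count for QT/QTc increases

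*Protocol*

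**What the plan says.** Protocol Section 9.4.5 and Table 3 footnote o require ECGs at Screening, at the end-of-treatment visit (Week 49), and after the first administration, "prior to dosing at Week 2 for CAM2038 q1w or Week 5 for CAM2038 q4w". Section 9.4.5 adds that "ECGs will also be performed in connection to dose increases (excluding the initial dose titration and booster injections"), and that ECGs follow "after intake of QT-extending drugs or CYP3A4 inhibitors". No time since injection is attached to any of these.

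Section 5.4 describes onset "with maximum plasma concentrations established within 24 hours after injection". Table 1 in Section 5.3, "Plasma Concentrations of Buprenorphine (Geometric Mean) After Single Subcutaneous Administration of CAM2038 q1w", gives values in healthy subjects up to 36 hours.

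For new entrants, Section 7.1.2.1 says "All subjects will return to the clinic on Day 2 to ensure tolerability". In Table 3 the Day 2-7 column is blank for ECG and for vital signs, and the marks it does carry are defined as optional visits. Respiratory rate is measured only as part of vital signs (footnote n: "Includes temperature, blood pressure, pulse rate, respiration rate").

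SAP Section 11.1.6 summarises absolute QT, QTcB and QTcF categories at each visit and also over all visits. For changes it says only that "increases in these parameters of <30 msec, 30 to <60 msec and greater than/equal to 60 msec will be summarized at each visit".

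**The concern.** The primary objective is safety. The protocol itself treats QT prolongation as a risk (exclusion criterion 12, triggered ECGs) and also respiratory and CNS depression (Section 8.7). SAP Section 11.0 rests the safety evaluation partly on changes in vital signs and ECG.

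If the fixed ECGs come at the end of the dosing interval and the others have no recorded time since injection, the ECG tables (14.3.18 and 14.3.19) cannot tell the reader which concentrations they describe. The vital-sign tables (14.3.17) share the labelling problem. Unlabelled, they could be taken to cover the whole interval, including the peak.

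The SAP gap adds to this. Triggered ECGs are the readings most likely to show a change, and they occur in different weeks for different patients. A by-visit table scatters them over many rows.

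**Working it through.** **1. Time of peak, from Table 1 (ng/mL).**

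| q1w dose | Highest value | Time | 36 h / 24 h |
|---|---|---|---|
| 8 mg | 1.65 | 24 h | 1.11/1.65 = 0.67 |
| 16 mg | 2.84 | 10 h and 24 h | 2.02/2.84 = 0.71 |
| 32 mg | 5.00 | 24 h | 3.76/5.00 = 0.75 |

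This agrees with the Section 5.4 statement of a maximum within 24 hours. Table 1 has no q4w data, so for q4w the peak time rests on Section 5.4 alone.

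**2. Elapsed time from first injection to first on-treatment ECG** (visit windows from Table 3: ±3 days weekly, ±7 days monthly).
- q1w, Week 2: 7 × 24 = 168 h; window (7 − 3) × 24 = 96 h to (7 + 3) × 24 = 240 h.
- q4w, Week 5: 28 × 24 = 672 h; window (28 − 7) × 24 = 504 h to (28 + 7) × 24 = 840 h.

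**3. Week 49 ECG in a subject who completes treatment.** The last q4w injection is at Week 45 (Table 3 footnote g), so the ECG is nominally 28 days later. After a last q1w injection at Week 48 it is nominally 7 days later.

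**4. Readings that may fall nearer the peak.**
- A new entrant may receive an extra 8 mg injection on Days 4 to 7 (Section 7.1.2.1). A Day 8 pre-dose ECG is then (8 − day) × 24 = 96, 72, 48 or 24 h after that injection.
- Dose-increase ECGs have no stated time. Dose changes are made at scheduled visits (Section 7.1.2.3), and no visit a day later is scheduled. The ECG could be at the same visit, the next one, or an unscheduled one.
- Vital signs are due on Day 1 and at the weekly or monthly visits, with no stated order relative to the injection.

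None of these is planned or labelled as a near-peak reading.

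**5. What the by-visit increase table can show.** Let n(v) be the number of patients with an increase of at least 60 msec at visit v. The number of patients with such an increase at any visit lies between the largest n(v) and the sum of the n(v). One patient at each of two visits could be one patient or two. The planned table cannot settle this; an any-visit row can.

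**6. What cannot be computed.** Table 1 stops at 36 h and no trough value is tabulated. A peak-to-trough ratio, and so the size of any underestimate, does not follow from the documents.

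**The case against.** A reader might infer that QT and respiratory effects are never measured near peak. The documents do not support that. Triggered ECGs and Day 1 vital signs have no fixed time, and a Week 2 ECG can follow a late Week 1 booster by 24 to 96 hours.

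A reader might also extrapolate the fall from 24 to 36 hours, or assume a trough fraction, and conclude that the ECGs see only a given share of the peak effect. That is not supported either. The values are single-dose and from healthy subjects, and the same sentence in Section 5.4 that gives the 24-hour peak goes on to claim reduced variation and stable levels for at least 7 days (q1w) and 28 days (q4w).

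It is also fair to say that this is a long-term safety study, not a concentration-QT study. Adverse events are elicited at every clinic visit, so respiratory symptoms on Day 2 can be reported, though respiratory rate is not measured. Individual ECGs appear in Listing 16.2.12. The documents do not describe ECG timing in the earlier studies, so a gap in the whole programme cannot be shown.

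Finally, a Day 2 ECG would have limited reach. It would cover new entrants after a first 16 mg dose, whose single-dose peak in Table 1 is 2.84/5.00 = 57% of the 32 mg peak. It would not cover transfers from SL buprenorphine, q4w starters or steady state.

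These points limit the claim and argue against insisting on an added ECG. They leave in place the missing time-since-injection label, the absence of a planned reading at the stated peak, and the missing any-visit row for increases.

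**Conclusion.** The point holds in a limited form. The fixed on-treatment ECGs fall nominally 7 days (q1w) or 28 days (q4w) after an injection, against a stated peak within 24 hours. Triggered ECGs have no stated time after dose, and no ECG or vital-sign set is scheduled at the peak. The numerical effect on the results is unknown and cannot be derived from the documents. The consequence is one of interpretation: the planned ECG and vital-sign tables do not establish what happens at peak concentration and should not be presented as if they did.

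The SAP gap is firm and needs no pharmacokinetic assumption: no table gives the number of patients whose largest QT/QTc increase reached 30 or 60 msec.

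The timing conclusion assumes visits at nominal times, a q4w peak as stated in Section 5.4, and a Day 2 visit about 24 hours after dosing, for which no clock time is given.

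**What to change.** 1. **SAP Section 11.1.6.** Add an overall (any-visit) row to the QT, QTcB and QTcF increase categories. Count each patient once, by the maximum increase from baseline over scheduled and triggered ECGs. Cost: one row per parameter.
2. **Time since injection.** Record or derive it for every ECG and vital-sign set. Elapsed days follow from the injection and assessment dates; same-day readings need a clock time or a pre/post-injection flag. Label the Week 2, Week 5 and Week 49 ECG results as end-of-interval. Cost: at most one CRF field and a table label.
3. **Day 2.** Reconcile Section 7.1.2.1, where all new entrants return, with Table 3, where Day 2-7 is optional. Mark vital signs, including respiratory rate, at that visit. Cost: a few minutes per new entrant. It does not cover transfers from SL buprenorphine, q4w starters or steady state; for them the remedy is item 2.
4. **Dose-increase ECGs.** Reconcile *after* (Table 3 footnote o) with *in connection to* (Section 9.4.5), so that sites know when the ECG is due.

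An added Day 2 ECG is optional; the point does not depend on it.
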